#### Statistical analysis plan

The data were analyzed using intention-to-treat principles with the SPSS version 20.0 for Windows. The last observation carried forward imputation was used for imputing missing data. Descriptive statistics were used to summarize and report data. All outcome data were assessed for normality using the Kolmogorov-Smirnov test. Repeated measures analysis of variance with Bonferroni post hoc comparisons was used to compare changes in outcome variables between groups. The equivalent non-parametric tests (i.e. Friedman test and Kruskal Wallis test) were used if data were not normally distributed. Numbers, percentages, mean, standard deviation, median, interquartile range, and p-values were reported. All analyses were tested with a

significance level of  $p<0.05$ .

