## Introduction

Puerperal mastitis is one of the most commonly reported problems during breastfeeding (1-3). Women frequently report breast pain, tenderness, redness, engorgement, fever, malaise, chills, lethargy, sweating, headache, nipple damage and a hot spot on the affected breast (4-6). These highly distressing symptoms may severely impact on a woman's daily activities and quality of life and might lead to the premature cessation of exclusive breastfeeding, which may have significant impact on infant health and survival.

The role of physical therapy in reducing pregnancy/postpartum-related disorders including breast problems is gaining momentum and importance in obstetrics (7). However, to date, only low-level evidence has shown positive effects of breast massage, a physical technique, on pain, milk supply and symptom relief in women with breastfeeding problems (7). This is encouraging, however further research is needed to explore whether physical therapy is effective to reduce symptoms of

puerperal mastitis. Therefore, the aims of this study were to explore clinical effects of therapeutic ultrasound, education and massage on mastitis symptoms and to compare the effectiveness of therapeutic ultrasound, education and massage versus usual obstetric care and sham ultrasound treatment on patient-centered outcomes in the short- and medium-term.

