## Methods

A randomized controlled trial was conducted from May 2021 to April 2023. Postpartum lactating women aged from 21 to 45 with breast symptoms were recruited through the Obstetrics and Gynecology Clinic of National Cheng Kung University Hospital, the postpartum care centers, websites and community. Eligible participants were randomly allocated to the ultrasound group, sham group, or usual care group. Participants allocated to the ‘Ultrasound’ arm of the trial participated in four one-hour treatment sessions with the physical therapist over one week. The treatment included educating the patient about mastitis and self-management strategies, treating with therapeutic ultrasound and administering and teaching breast massage. Participants allocated to the ‘Sham’ group received the same education and breast massage sessions as described above. In addition, the sham control group received 5 minutes of ‘sham’ ultrasound at 0 W/cm^2 intensity from a physical therapist. Participants

allocated to the ‘Usual care’ group received usual obstetric care, which included verbal advice/printed patient information regarding mastitis and breastfeeding from the medical or nursing staff. The outcome measures including severity of breast symptoms (breast and nipple pain, breast engorgement), breast hardness, body temperature, breast temperature, breastfeeding self-efficacy, and milk volume were assessed at baseline, immediately post-intervention, and at 3 months following baseline. The acceptability of the intervention program and adverse events were recorded immediately post-intervention and at 3 months following baseline.

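### The collected baseline is not used as a covariate, and the Bonferroni comparisons are tied to no ANOVA term or visit; baseline-adjusted arm differences at each visit would add precision without new data

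*Combined protocol and SAP*

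**What the plan says.** The aim, in the Introduction, is to compare the ultrasound programme with usual care and with sham "on patient-centered outcomes in the short- and medium-term". According to Methods, "Eligible participants were randomly allocated to the ultrasound group, sham group, or usual care group", and the efficacy outcomes (breast symptoms, hardness, body and breast temperature, self-efficacy, milk volume) "were assessed at baseline, immediately post-intervention, and at 3 months following baseline". The sham arm "received the same education and breast massage sessions as described above".

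The Statistical analysis plan then states: "Repeated measures analysis of variance with Bonferroni post hoc comparisons was used to compare changes in outcome variables between groups". For other outcomes, "The equivalent non-parametric tests (i.e. Friedman test and Kruskal Wallis test) were used if data were not normally distributed". For missing values, "The last observation carried forward imputation was used for imputing missing data".

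No covariate or baseline adjustment is named anywhere. The plan does not say whether the Bonferroni comparisons follow the group-by-time interaction or the group main effect, or at which visit they are made. The list of reported items contains p-values and descriptive statistics, but no arm difference and no confidence interval.

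**The concern.** Baseline enters the planned ANOVA only as one level of the time factor. A change score subtracts the whole baseline value. A covariate model subtracts only the part that predicts follow-up, so it leaves less residual noise unless the slope of follow-up on baseline is exactly 1.

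The aim asks about two time frames, so the useful quantity is an arm difference at each visit. Precision matters most for ultrasound versus sham: both arms receive the same education and massage, so the difference to be detected may be small. The open choice of ANOVA term also matters, because one of the possible terms estimates a diluted effect.

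**Working it through.** **Inputs from the documents.** Three arms, hence three pairwise comparisons; one baseline and two follow-up visits; significance level 0.05 (sidedness not stated, two-sided assumed).

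**Inputs not in the documents.** The correlation r between baseline and follow-up, the SDs, the arm sizes, the effect size and the dropout rate. The plan states no sample size or power, so there is no figure to reproduce. All values of these inputs below are assumptions.

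**1. Precision at one visit, equal SDs (SD = 1).** Per-woman variance:
- change score: 2(1−r)
- baseline-adjusted: 1−r²
- ratio: (1−r²)/[2(1−r)] = (1+r)/2

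| r | 0.3 | 0.5 | 0.7 | 0.9 |
|---|---|---|---|---|
| Variance ratio | 0.65 | 0.75 | 0.85 | 0.95 |
| Interval-width ratio (square root) | 0.81 | 0.87 | 0.92 | 0.97 |

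**2. Unequal SDs.** With k = follow-up SD / baseline SD, the ratio is k²(1−r²)/(k²+1−2rk).

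| r | 0.3 | 0.5 | 0.7 | 0.9 |
|---|---|---|---|---|
| k = 0.8 | 0.50 | 0.57 | 0.63 | 0.61 |
| k = 1.25 | 0.78 | 0.89 | 0.98 | 0.95 |

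Denominator minus numerator is (1−rk)², which is never negative. In large samples the adjusted difference is therefore never less precise, and the gain vanishes when rk = 1.

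**3. Small samples.** In simulations with three arms, complete normal data and 6,000 runs per setting, the variance ratio at r = 0.3/0.5/0.7 was 0.69/0.78/0.89 with 10 per arm and 0.67/0.76/0.87 with 30 per arm. Type I error was close to 5% for both methods. These runs compared single-visit estimators; they contained no repeated measures ANOVA, no LOCF and no switch after a normality test.

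**4. Illustrative power.** Ultrasound versus sham at one visit, noncentral t, noncentrality d/√(2V/n), where V is the per-woman variance from step 1; two-sided 0.05/3; 3n−4 degrees of freedom adjusted, 3n−3 for change score.

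| Assumed n per arm, d | Adjusted, r = 0.3/0.5/0.7 | Change score, r = 0.3/0.5/0.7 |
|---|---|---|
| 30, 0.75 | 73/82/95% | 51/68/90% |
| 20, 0.75 | 51/61/80% | 33/47/72% |
| 30, 0.5 | 35/42/61% | 22/31/53% |

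With n = 30 and d = 0.75, both exceed 99% at r = 0.9.

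**5. If the comparisons follow the group main effect.** The arm means then average baseline (expected difference 0) with two follow-up visits (constant difference d): (0 + d + d)/3 = 2d/3. A true 0.75 is estimated as 0.50. This is a shift in what is estimated, not only a loss of precision.

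**6. What LOCF does to a comparison of changes.** A woman with no follow-up value is given a change of zero. Suppose mean changes of −2.75 and −2.00 SD, a true difference of 0.75.
- 15% lost in each arm: 0.85 × 2.75 − 0.85 × 2.00 = 0.64
- 10% and 20% lost respectively: 0.90 × 2.75 − 0.80 × 2.00 = 0.88 (0.875 before rounding)

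The bias can go either way, and adding a covariate is not a remedy for it.

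**The case against.** Comparing changes between randomised arms is an accepted analysis, and the size of the benefit here cannot be established. Every correlation, SD, arm size and effect size above is assumed, and the tabulated variance gain runs from 2% (k = 1.25, r = 0.7) to 50% (k = 0.8, r = 0.3). Outcomes sent to Friedman or Kruskal-Wallis gain nothing in these calculations, and how many those are is unknown. The trial is described as already run ("A randomized controlled trial was conducted from May 2021 to April 2023"), so a new model can only be post hoc and adds unplanned estimates. All of this stands. It limits the claim to an efficiency improvement shown beside the planned result.

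A second objection is that precision gained from the covariate can be lost if LOCF is dropped at the same time. At an assumed 15% without follow-up, variance rises by 1/0.85 = 1.18, and 0.85 × 1.18 = 1.00, which cancels the whole gain at r = 0.7. LOCF's apparent precision is spurious, so this is no defence of LOCF. It does mean that the covariate must be judged with the missing-data rule held fixed.

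Two stronger readings are tempting. A reader might infer that the planned analysis is valid as it stands and loses only precision. The documents do not support that: unbiasedness holds for complete data, the plan imputes by LOCF, step 6 shows how that can distort the difference, and the simulations did not test it. A reader might also infer that ultrasound versus sham isolates the ultrasound. Methods matches the two arms on education and massage but says nothing about blinding, so the contrast should be described only as matched on those components.

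**Conclusion.** The point holds as an improvement worth making, not as an error in comparing changes. The collected baseline goes unused as a covariate. Using it at each visit would, in large samples and with the same data, never be less precise than the change score. At equal SDs the variance falls by 35%, 25%, 15% or 5% at assumed r of 0.3, 0.5, 0.7 or 0.9; the size in this trial is unknown.

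The undefined comparison is a second, separate weakness. The wording about changes favours an interaction or change contrast, but nothing excludes the group main effect, under which a constant effect is reported at two-thirds of its size.

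The gains do not carry over to outcomes analysed by Friedman or Kruskal-Wallis. Acceptability and adverse events were not recorded at baseline, so the point does not apply to them.

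**What to change.** Add a supplementary analysis, labelled post hoc and shown beside the original ANOVA result (or beside the Friedman/Kruskal-Wallis result where that was used):

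1. State which ANOVA term and visit the original Bonferroni comparisons referred to.
2. Model the post-intervention and 3-month values with baseline-by-visit, arm, visit and arm-by-visit terms, and an unstructured within-woman covariance.
3. Report ultrasound–sham, ultrasound–usual care and sham–usual care differences at each visit, with Bonferroni intervals for three comparisons within a visit (0.05/3, that is 98.3% intervals).
4. Fit this first to the same LOCF data as the original ANOVA, so that only the covariate changes.
5. As a separate sensitivity analysis, fit it to observed data without LOCF, and give by arm the number of women with no follow-up value.

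The cost is analysis and reporting time. No new data or participants are needed, and the planned result stays in place.

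### Bonferroni over the three pairs of arms is valid but needlessly conservative: Holm or a closed test gives the same 5% familywise control, per outcome and visit, with more power

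*Combined protocol and SAP*

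**What the plan says.** The Methods section describes a three-arm randomised trial: "Eligible participants were randomly allocated to the ultrasound group, sham group, or usual care group". The second aim in the Introduction sets the ultrasound package against two comparators: "versus usual obstetric care and sham ultrasound treatment on patient-centered outcomes in the short- and medium-term". Outcomes "were assessed at baseline, immediately post-intervention, and at 3 months following baseline", so each outcome yields two changes from baseline.

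The Statistical analysis plan compares the arms as follows: "Repeated measures analysis of variance with Bonferroni post hoc comparisons was used to compare changes in outcome variables between groups". The level is 0.05. The SAP does not say which comparisons form the Bonferroni family, whether tests are two-sided, or why Bonferroni was chosen. For non-normal data it says: "The equivalent non-parametric tests (i.e. Friedman test and Kruskal Wallis test) were used if data were not normally distributed". No pairwise step or adjustment is named on that route. On reporting: "Numbers, percentages, mean, standard deviation, median, interquartile range, and p-values were reported". Confidence intervals are not listed. The documents give no sample size, power, effect size or standard deviation.

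**The concern.** Bonferroni makes no use of the fact that the three pairwise null hypotheses are logically linked. If any two of them are true, all three arms are equal, so the third is true as well. A procedure that uses this link can test the pairs less strictly and keep the same error guarantee.

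The contrast most exposed is ultrasound v sham. Both of those arms receive the same education and massage, so it is the only comparison that isolates ultrasound. Its effect is plausibly the smallest of the three, and under Bonferroni it must reach 0.0167. A real effect is then more likely to be missed than it need be.

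**Working it through.** The plan states no figure to reproduce, so the check has two parts: the error-control argument, which needs no assumed effect, and an illustration of power, which does.

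**Inputs.** From the documents: three arms, hence three pairs; level 0.05; two follow-up visits. Assumed: equal allocation, two-sided tests, normal data with common variance, and a Bonferroni family of the three pairs.

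**1. Error control.** Only three configurations contain a true null.
- *All arms equal.* A closed test errs only if the global three-arm test rejects, which has probability at most 0.05.
- *Exactly one pair equal.* The only possible error is rejecting that pair, which is tested at 0.05, so the probability is at most 0.05.
- *Exactly two pairs equal.* This is impossible with three arms.

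A global test at 0.05 followed by each pair at 0.05 therefore controls familywise error strongly. Either of two gates will do: the 2-df F test, or smallest pairwise p < 0.05/3 (valid because 3 × 0.0167 = 0.05). The gate is essential. Simulated without it, the three pairs at 0.05 give a familywise error of 0.12 when all arms are equal.

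**2. Cost of the stricter level for a single pair.** By the normal approximation, n per arm = 2(z₁₋α/₂ + z_power)²/d².
- At 80% power and α = 0.05, z₁₋α/₂ + z_power = 1.960 + 0.842 = 2.802.
- At α = 0.0167 it is 2.394 + 0.842 = 3.236. The ratio of sample sizes is (3.236/2.802)² = 1.33.
- For d = 0.5 SD, n rises from 63 to 84 per arm. For d = 0.8 SD, it rises from 25 to 33.
- With n held fixed, power falls from 80% to Φ(2.802 − 2.394) = Φ(0.408) = 66%.

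**3. Simulation of one outcome at one visit** (40 per arm, true difference 0.626 SD, 200,000 or more replicates):

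| Quantity | Bonferroni | Holm | Closed F |
|---|---|---|---|
| Power, ultrasound v sham, if sham = usual care | 65% | 68% | 75% |
| Power for both ultrasound contrasts, same setting | 49% | 56% | 67% |
| Power, ultrasound v sham, if graded in equal steps of 0.626 SD | 65% | 78% | 79% |
| Familywise error, all arms equal | 4.3% | 4.3% | 4.9% |
| Error on a single true-null pair, third arm different | 1.7% | 3.2% | 4.9% |

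Two other settings give the same pattern: 25 per arm with 0.8 SD, and 63 per arm with 0.5 SD. When one arm differs, per-pair power is about 65% with Bonferroni, 73% with the closed test gated on the smallest p, and 75% with the closed F test. If the step from sham to ultrasound is only half that size (0.4 or 0.25 SD), power for that contrast is low throughout: about 16% with Bonferroni and 27% with closed F.

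**4. Does the alternative ever lose a Bonferroni rejection?** Holm and the closed test gated on the smallest p never did. The F-gated version did in up to about 0.6% of replicates.

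**5. Choice of gate.** Suppose the arms differ at one visit and are equal at the other. An overall group-by-time F test across visits is then significant because of the first visit. At the null visit, the three pairs at 0.05 have a familywise error of about 12%, against 4.3% for Bonferroni.

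**The case against.** Bonferroni is a valid and standard method, it needs no gate, and choosing among valid methods can look like preference. That it is valid stands, and a reader should not infer that the plan has an error-rate fault. The preference argument is weaker. Holm and the closed test gated on the smallest p keep every Bonferroni rejection and add others at the same guarantee. Bonferroni's usual advantage, simple simultaneous confidence intervals, carries little weight where no intervals are planned.

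A second objection is that loosening the pairwise tests is unwise when wider multiplicity is unaddressed. Methods lists at least six outcome measures at two follow-ups, so at least 12 analyses. If ultrasound and sham are truly equal, usual care differs, and the analyses are independent (an assumption; correlation would lower both figures), the chance of at least one false ultrasound v sham claim is about 1 − 0.983¹² = 19% at the Bonferroni rate. It is 1 − 0.95¹² = 46% at 5%. That trade-off is real and should be stated. It does not justify Bonferroni over arms, which was never a control over outcomes or visits.

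Third, the trial ran from May 2021 to April 2023 and the SAP is in the past tense. This bears on how a changed analysis is labelled, not on whether the point is right.

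Other stronger readings are tempting. One is that Bonferroni brings no benefit at all and the F-gated test beats it outright; the rare lost rejections rule that out. Another is that all pairs may simply be tested at 0.05; without the gate they may not. A third is that the aims make sham v usual care redundant. The second aim names only the two ultrasound contrasts, but the SAP does not limit its comparisons to those, and sham v usual care bears on massage and education.

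**Conclusion.** The point holds as one of efficiency. For each outcome at each visit, the Bonferroni step gives up power that Holm or a closed test would keep under the same 5% familywise guarantee. The error-control result does not depend on the effect size or standard deviation.

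The size of the gain does. Under the assumptions above, it is 3 to 13 percentage points for ultrasound v sham with Holm (65% to 68%, or 65% to 78%). With the closed F test it is 10 to 14 points (65% to 75%, or 65% to 79%). The 0.0167 threshold is itself an inference, since the SAP leaves the family undefined. The documents do not support a claim that this trial missed a real effect or was underpowered, because they give neither a sample size nor a target difference.

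**What to change.** Define the family as the three pairs of arms for one outcome's change at one visit, and replace the Bonferroni step with one of these:

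- **Holm-adjusted pairwise comparisons.** This is the simpler choice and can be applied by hand to three unadjusted p-values.
- **A closed test, for more power.** Test each pair at 0.05 only if a three-arm global test of the same outcome's change at the same visit is significant at 0.05. The gate may be the 2-df F test or smallest pairwise p < 0.0167, and should be fixed in advance. The second never loses a Bonferroni rejection; the first rarely does.

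State that the overall group-by-time F test across visits is not the gate. On the non-parametric route, use Kruskal-Wallis on the change at that visit as the gate, or Holm on the pairwise rank tests, and name those pairwise tests.

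The cost is a few sentences in the SAP and routine tests on the same data. Simultaneous intervals would be less simple if they were added later. The error rate for a single true-null pair rises from about 1.7% to at most 5%. Multiplicity over outcomes and visits needs its own provision. If results have already been seen, report the planned Bonferroni analysis and label the new one post hoc.

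### The Friedman and Kruskal-Wallis fallback does not replace the ANOVA of change between arms, and names no rank test for ultrasound versus sham or versus usual care

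*Combined protocol and SAP*

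**What the plan says.** The Introduction sets the comparison as the ultrasound package "versus usual obstetric care and sham ultrasound treatment on patient-centered outcomes in the short- and medium-term". Under Methods there are three arms ("Eligible participants were randomly allocated to the ultrasound group, sham group, or usual care group"), and the sham arm "received the same education and breast massage sessions as described above". The efficacy outcomes "were assessed at baseline, immediately post-intervention, and at 3 months following baseline", so each has a baseline value and two follow-up values.

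The Statistical analysis plan gives the main method: "Repeated measures analysis of variance with Bonferroni post hoc comparisons was used to compare changes in outcome variables between groups". The route to the fallback is a normality check: "All outcome data were assessed for normality using the Kolmogorov-Smirnov test". The fallback itself is one sentence: "The equivalent non-parametric tests (i.e. Friedman test and Kruskal Wallis test) were used if data were not normally distributed". It does not say which test serves which question, whether the response is the score or its change, which visit is tested, or how arms are compared in pairs.

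**The concern.** The ANOVA sentence covers visits, arms and pairwise comparisons together. The fallback sentence replaces it with two one-factor tests and calls them *equivalent*. Any outcome that fails the normality check therefore loses the joint analysis. As written, it also loses the pairwise step that the aim needs.

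That step matters because of the design. Ultrasound and sham differ in the ultrasound; both differ from usual care in the education and massage. A single three-arm p-value cannot tell the two effects apart. If pairwise tests were added informally at 0.05 each, the familywise error, treating the tests as independent, would be 1 − 0.95² = 9.8% for two contrasts or 1 − 0.95³ = 14.3% for three.

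There is also a loss of efficiency. The trial collects a baseline for these outcomes, and neither a raw follow-up score nor a simple change score makes the best use of it.

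**Working it through.** The plan gives no sample size, SD, effect size or power, so there is no stated figure to reproduce.

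**Inputs from the documents:** three arms, two follow-up visits, two contrasts in the aim, significance level 0.05.

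**Inputs assumed:** 15, 30 or 50 women per arm; baseline to follow-up correlation 0.3 to 0.7; two non-normal outcomes. The first is skewed (exponential, SD 2). The second is a 0–10 integer score with a floor: baseline round(6 + 2Z), follow-up round(2 + 2Z), clipped to 0–10. Zeros at follow-up occur when 2 + 2Z < 0.5, that is Z < −0.75, or 23%. A 1.5-point latent shift is about 1.1 points observed on this score. Simulations used 4,000 trials per cell unless stated, and ranges run over the correlation.

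**1. What each method can see**

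| Method | Visit | Arm | Pairwise step named |
|---|---|---|---|
| Repeated measures ANOVA | yes | yes | yes (Bonferroni) |
| Friedman | yes | no | no |
| Kruskal-Wallis | no | yes, omnibus | no |

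This follows from the definitions of the tests. As an illustration, with lognormal data, 20 or 40 per arm, and every arm improving equally (0.8 SD after treatment, 1.2 SD at 3 months), pooled Friedman was significant in 100% of trials at both sizes. Kruskal-Wallis on change immediately after treatment rejected in 4.4% and 4.5%.

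**2. What the three-arm p-value leaves open**

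Set ultrasound equal to sham and usual care 1.5 points worse. Kruskal-Wallis on the follow-up score was significant in 79–80% (15 per arm) and 99% (30) of skewed trials, and in 45–46% and 78–80% with the floor. A two-arm, baseline-rank-adjusted contrast of ultrasound versus sham at 0.025 was positive in 2.1–3.2%, close to nominal. The omnibus result is right that the arms differ; only the contrast shows that ultrasound adds nothing in this scenario.

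**3. Use of baseline**

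On a linear scale with equal variance σ² at both visits and correlation ρ, the variance per woman is σ² for the follow-up score, 2σ²(1 − ρ) for change and σ²(1 − ρ²) after baseline adjustment. At ρ = 0.3 the multipliers of σ² are 1, 1.40 and 0.91; at ρ = 0.7 they are 1, 0.60 and 0.51. Adjustment is the smallest in both cases.

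Rank versions, three-arm power at 0.05, one arm better by 1.5 points:

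| Outcome, per arm | Kruskal-Wallis, follow-up | Kruskal-Wallis, change | Quade |
|---|---|---|---|
| Skewed, 15 | 73% | 53–87% | 77–94% |
| Skewed, 30 | 96% | 84–100% | 97–100% |
| Floor, 15 | 44–45% | 23–46% | 48–69% |
| Floor, 30 | 78–79% | 48–78% | 82–96% |

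The Quade test held its level (4.5–5.7%). If the shift is instead upward in usual care (floor score, 15 per arm, 1,500 trials per cell), the figures are 48–49%, 33–63% and 52–74%, so the ordering is the same.

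For a single contrast at 0.025 (5,000 trials per cell), two-arm Quade against Mann-Whitney on follow-up gave, for skewed data, 67–87% v 61–63% (15 per arm) and 95–100% v 92–93% (30). With the floor it gave 35–54% v 33% and 69–88% v 65–66%.

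**4. What hangs on the unstated response**

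With one arm shifted by 1.5 points, Kruskal-Wallis on follow-up and on change gave opposite verdicts on the same data in 25–32%, 4–14% and 0–2% of skewed trials (15, 30, 50 per arm), and in 37–46%, 31–42% and 8–28% with the floor.

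**5. Error control of the proposed contrasts**

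In skewed data with usual care worse, ranking over all three arms gave 3.3–4.8% false positives for ultrasound versus sham at a nominal 2.5%; fitting on the two arms alone gave 2.2–3.0%. Two contrasts at 0.025 bound the error at 2 × 0.025 = 0.05 within one outcome and visit. Over both visits the bound is 4 × 0.025 = 0.10, or 1 − 0.975⁴ = 0.096 if the tests were independent.

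**The case against.** The main sentence speaks of comparing changes, and the aim speaks of short and medium term. Read together, they point to change from baseline at both follow-up visits. That stands as the likeliest reading, so the response and visit are not wholly open; but the fallback sentence does not state it. Likewise, a reader may carry the Bonferroni step over, since *equivalent* refers to a method that includes it. That is possible, but the list of substitutes names two tests and no pairwise rank procedure.

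Three stronger inferences should be resisted.

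- A reader might take the 45–99% rejection rates in step 2 as false positives. They are not: usual care truly differs there, and any good omnibus test should reject.
- A reader might infer that Kruskal-Wallis is invalid, or that disagreement between the two versions shows bias. Under randomisation the test is valid, and two tests of moderate power will often disagree.
- A reader might infer that Friedman was offered as evidence of a treatment effect. The documents do not say so.

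It is also fair that stating the response and visit and naming an adjusted pairwise rank test would close the specification gap without Quade. The case for Quade is efficiency. Its gain is small when the baseline correlation is low (35% v 33% for one contrast, floor score, 15 per arm) or arms are large (almost none for skewed data at 50 per arm).

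**Conclusion.** The point holds. Friedman and Kruskal-Wallis are not equivalent to the planned ANOVA, and as written the fallback supplies no test of ultrasound versus sham or ultrasound versus usual care. The finding on what the tests measure rests on their definitions and needs no assumed data. The power and disagreement figures rest entirely on the assumed sample sizes, distributions, shifts and correlations, and show direction and rough size only. How many outcomes reached the fallback cannot be known from the documents, so no particular trial result can be said to be affected. This is worth correcting because a better method is available from data already collected; it is not grounds for calling the fallback p-values wrong.

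**What to change.** For any non-normal outcome with a baseline value:

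- At each follow-up visit, use a rank ANCOVA adjusted for baseline rank (Quade) as the between-arm test.
- Add two contrasts, ultrasound versus sham and ultrasound versus usual care, each re-ranked and fitted on its own two arms at 0.025.
- State that this controls error within one outcome and visit only (up to about 10% across both visits), or name one visit as primary.
- Use Friedman only to describe change over time, and delete the word *equivalent*.

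Acceptability needs separate handling. Methods records it only after treatment ("The acceptability of the intervention program and adverse events were recorded immediately post-intervention and at 3 months following baseline"), so there is no baseline to adjust for. It concerns a program that usual care did not receive. State the visit and compare only ultrasound with sham, unless usual care supplied comparable data.

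Methods describes the trial as already conducted, so label the re-analysis post hoc and report it beside the tests already run. Quade yields a p-value and no difference in points, so show medians or a median difference with it. The cost is a small re-analysis (rank, regress on baseline rank, compare residuals) and a few sentences of text, with no new data.
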